Patient participants: Basic demographic data of age, sex, height and weight will be collected at baseline. Key baseline covariate factors to be collected at baseline are pain duration, pain location for the actual presenting MSKP complaint, number of other sites with MSKP, previous health care interventions for presenting MSKP complaint in the last 3 months, previous health care interventions for other MSKP sites in the last 3 months, number of comorbidities, analgesic medication use (type and consumption), level of education, employment and self-reported sick leave for the presenting MSKP complaint.

Physiotherapist participants: Basic demographic data of age, sex, department, level of education and number of years working as a physiotherapist will be collected prior to the start of patient recruitment.

Patient Reported Outcome Measures (PROMs)

For information on the time points for data collection of each PROM and PREM see patient participant timeline and Figure 4.

Primary outcome measures

Both primary outcome measures will be collected and analysed via group mean change from baseline. Primary outcome analysis time points are 1) Baseline to 24 hours post initial physiotherapy consultation and 2) Baseline to three months.

- Pain intensity

Pain intensity is chosen as a primary outcome for this study as it is a core outcome measure for intervention studies on pain (Chiarotto et al., 2018). Average pain intensity in the previous 24 hours will be measured using a numerical rating scale (NRS) (0-11 from 0 = no pain to 10 = worst imaginable pain) (Jensen et al., 1999). The average pain intensity NRS rating related to the past 24 hours has been chosen to reduce overlap of the ratings at the separate data collection time points. Consensus from the VIII International Forum on Primary Care Research on LBP and the median of study results from systematic reviews of pain intensity ratings in acute and chronic pain suggests that the minimal clinically important difference (MCID) for pain intensity is two points (Olsen et al., 2017; Olsen et al., 2018; Ostelo et al., 2008).

- Pain self-efficacy

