NRS pain intensity and pain self-efficacy will be additionally analysed as secondary outcomes for within group and between group differences for data collected at non-primary outcome time points. In addition to the primary outcome of average pain intensity, worst pain intensity and best pain intensity in the previous 24 hours will be measured using two NRS scales (0-11 from 0 = no pain to 10 = worst imaginable pain) (Jensen et al., 1999). Both primary outcome measures will be additionally analysed as a secondary outcome for proportion of responders based on study specific MCIDs. The MCIDs for the two primary outcomes will be calculated for interpretation of the within and between-group differences. The MCIDs will be calculated for the whole cohort using an anchor method based on the Global rating of change scale (GRoCs) scores (Revicki et al, 2008).

- *MSKP illness perceptions*

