This protocol outlines the principal features of the statistical analysis for this study. A full statistical analysis plan (SAP) has been published on Clinicaltrials.gov alongside this protocol and prior to the completion of patient recruitment (September 25, 2024).

Participant characteristics

Patient: Group characteristics will be presented using descriptive statistics. Baseline analysis between the intervention and control groups will be conducted to ensure the comparability of the groups.

Physiotherapist participants: Group characteristics (age, sex, department, highest educational level, number of years of clinical experience, adherence to protocol) will be presented using descriptive statistics.

Analysis of primary outcomes

Magnitude of within and between-group change on primary outcomes from baseline to 24-72 hours prior to the initial physiotherapy consultation, 24 hours post initial physiotherapy consultation and three months post-baseline will be analysed through mixed models. Data will be compared based on the 'intention to treat' (ITT) principle. Sensitivity analyses applying per-protocol, complier average causal effect (CACE) analyses and analyses applying study specific MCID associated with dichotomised anchor response on the GRoC will be explored. Sensitivity analyses to adjust for all measured baseline covariates will also be performed to investigate the presence of equipoise as the result of randomisation (Thabane et al., 2013).

Multiplicity/ type I (a) error

The outcomes collected in the study are considered as separate entities and, therefore, restrictive multiplicity penalisation of the model is not required (Dmitrienko & D'Agostino 2013). Adjustment will be used for repeated measures over time for separate test conditions.

Analysis of secondary outcomes

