on generalisability (Mercieca-Bebber et al., 2018). All outcome data will be compared based on the ITT principle. This means that all patients that have been randomised remain in the analysis based on their group allocation. In the event of substantial missing data, evaluation of the mechanisms for missing data will be used (Enders, 2011). Missing data will otherwise be handled under the missing at random assumption (Enders, 2011). Multiple Imputation or Maximum Likelihood estimation will be used assuming that missing data is conditional on variables included in the model. Imputation method considering missing at random or not missing at random will be used in the ITT analysis. Patients who cancel their initial physiotherapy consultation will be excluded from the PREM analysis but will remain in the study for PROM and healthcare register data analyses.

Study monitoring and harms

There will be no data monitoring committee since the study is independent from the sponsor and the intervention is implemented as an adjunct to usual physiotherapy management with low risk for unexpected adverse events. The PROMs included in the study are sensitive to worsening in the patients' condition. An internal pilot interim analysis was planned and conducted (February 29th, 2024) after approximately 50% of the initially planned sample (n = 229) had consented to the study and reported outcomes at time point two (72-24 hours prior to the initial physiotherapy consultation) and three (24 hours post the initial physiotherapy consultation). This interim analysis enabled evaluation of the viability of the a-priori sample size calculation and the recruitment frequency. The analysis utilised linear mixed models to investigate between group differences (effect size) for change from baseline to time points two and three for outcome. The significance level for the interim analysis was p=0.05. After interim sample size calculation, the sample size was adjusted slightly to take loss to follow-up into account. The sample size calculation is described under the protocol heading sample size. The trial would have been stopped if the internal pilot interim analysis could not be performed due to not attaining 50% of the sample size at Time point two and three within six months. No further interim analyses are planned.

Ancillary and post-trial care

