4. Three months post-baseline (primary time point two).

In addition, patients' reported experiences of the film and PROMs will be collected directly after exposure to the film in the intervention group. Secondary physiotherapist and patient reported experience measures (PREM) will be collected at time point 3. Healthcare register data relating to the three month study period for each participating patient will be collected after the completion of PROMs and PREMs data collection for all participants.

Data on the physiotherapists' adherence to the Pain-SMART strategy will be collected after all the first 450 included participants have had their first physiotherapy consultations (after time point three) approximately eight months after the inclusion of the first participant and prior to the start of patient inclusion to the qualitative phase of the trial. For primary and secondary PROM data the primary time points are defined as 24 hours post initial physiotherapy consultation (primary time point one) and three months post-baseline (primary time point two). The data collection is described in full in the trial protocol.

Outcome definitions

The primary and secondary outcomes are described in full in the trial protocol. Both trial arms have the following outcomes measured:

Primary outcomes

- Pain intensity

Self-reported average pain intensity in the previous 24 hours will be measured using numerical rating scales (NRS). Score range: 0-10 with 0 = no pain and 10 = worst imaginable pain.

- Time Frame: collected at baseline, 24 hours post initial physiotherapy consultation and at three months post-baseline.
- Calculation to derive outcome:
 - Between group mean change over time from baseline to 24 hours post initial physiotherapy consultation (primary time point one)
 - Between group mean change over time from baseline to three months post-baseline (primary time point two)

-Pain self-efficacy

Self-reported pain self-efficacy will be measured using the Pain Self-efficacy Questionnaire 10 (PSEQ-10). The PSEQ-10 is a 10-item questionnaire. Score range: 0-60, a higher score indicating greater pain self-efficacy.

- Time Frame: collected at baseline, 24 hours post initial physiotherapy consultation and at three months post-baseline.

- Calculation to derive outcome:
 - Between group mean change over time from baseline to 24 hours post initial physiotherapy consultation (primary time point one)

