 - Between group mean change over time from baseline to three months post-baseline (primary time point two)

Secondary outcomes

Patient reported outcome measures (PROMS)

-Pain intensity

Self-reported average pain intensity, worst pain intensity and best pain intensity in the previous 24 hours will be measured using numerical rating scales (NRS). Score range: 0-10 with 0 = no pain and 10 = worst imaginable pain.

- Time Frame: collected at baseline, 24-72 hours prior to the initial physiotherapy consultation, 24 hours post initial physiotherapy consultation and at three months post-baseline.
- Calculation to derive outcome:
 - Within group mean change in average pain intensity over time from baseline to follow-up three months post-baseline (all time points).
 - Between group mean change in average pain intensity over time from baseline to 24 -72 hours prior to the initial physiotherapy consultation.
 - Within and between group mean change in worst pain intensity total score over time from baseline to follow-up three months post-baseline (all time points).
 - Within and between group mean change in best pain intensity total score over time from baseline to follow-up three months post-baseline (all time points).

-Pain self-efficacy

Self-reported pain self-efficacy will be measured using the Pain Self-efficacy Questionnaire 10 (PSEQ-10). The PSEQ-10 is a 10-item questionnaire. Score range: 0-60, a higher score indicating greater pain self-efficacy.

- Time Frame: collected at baseline, 24 -72 hours prior to the initial physiotherapy consultation, 24 hours post initial physiotherapy consultation and at three months post-baseline.
- Calculation to derive outcome:
 - Within group mean change over time from baseline to follow-up three months post-baseline (all time points).
 - Between group mean change over time from baseline to 24 -72 hours prior to the initial physiotherapy consultation.

-Musculoskeletal pain (MSKP) illness perceptions

MSKP illness perceptions will be measured using the Brief Illness Perception Questionnaire (BIPQ). The BIPQ is a nine-item questionnaire where eight items are scored on a 11-point

NRS with anchor statements (score range 0-80, higher score reflecting higher perceived threat). One item is a free text question regarding believed cause of the MSKP (causal item).

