An internal pilot interim analysis was planned and conducted after 50% of the sample had reported outcomes at time point 2 (pre physiotherapy consultation) and 3 (primary time point one, post initial physiotherapy consultation). This to evaluate the viability of the a-priori sample size calculation and the recruitment frequency. The analysis utilised linear mixed models to investigate between group difference (effect size) for change from baseline to time points 2 and 3 in outcome. The significance level for the interim analysis was $p=0.05$. After interim sample size calculation, the sample size was slightly adjusted when taking loss to follow-up into account. The sample size calculation is described in the trial protocol. The trial would have been stopped if the internal pilot interim analysis could not be performed due to not attaining 50% of the sample size at Time point 2 and 3 within 6 months. No further interim analyses are planned.

Final analysis

The trial is planned to finish recruitment of new patient participants in Dec 2024 – Jan 2025. The final three-month follow-up data collection will therefore be in Mar - Apr 2025. All outcomes will be analysed collectively.

Analysis methods

Primary outcome analysis

-Pain intensity and Pain self-efficacy

Hypothesis testing for the two primary outcomes *pain intensity* and *pain self-efficacy* (score on average pain NRS in the last 24 hours and PSEQ-10) will be based on analysis of group mean change from baseline. Baseline scores and group mean change in primary outcome scores from baseline to primary time points one and two for the intervention and control groups and the between-group change for these time points will be presented as means and CI. The within and between-group change on primary outcomes from baseline to 24 hours post initial physiotherapy consultation and three months post-baseline will be analysed according to ITT principles using a maximum likelihood approach for mixed models adjusted for a relevant covariance structure. The models will be adjusted for baseline covariates where relevant. Baseline factors that will be analysed for potential covariate adjustment include: age, sex, educational level, employment, pain duration, number of pain sites, comorbidities, days to initial physiotherapy consultation, previous healthcare interventions, ÖMPSQ risk category, self-reported sick leave and analgesic medication consumption.

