The study specific minimal clinical important differences (MCID) for primary outcomes at primary time points will be calculated for interpretation of the within and between-group differences. The MCIDs will be calculated for the whole cohort using an anchor method (Revicki et al, 2008). A dichotomised anchor response on the GRoC (-5- 0 = not improved; 1-5 = improved) must at least have a small association with change in the primary outcome baseline to primary time points one and two. This will be applied in a receiver operator characteristic (ROC) curve analysing the area under the curve (AUC), specificity, sensitivity and Youden index to attain an optimal cut off point for the MCIDs. MCIDs will be presented in mean and SD.

[Secondary outcome analysis](#)

[Patient reported outcome analyses](#)

-Continuous variables

Hypothesis testing for secondary outcomes for *pain intensity*, *pain self-efficacy*, *MSKP illness perceptions (BIPQ)*, *reassurance of the benign nature of MSKP*, *traditional pain coping strategies (BPCI-2, sub-scale for pain coping strategies)*, *psychological flexibility (BPCI-2 sub-scale for psychological flexibility)*, and *physical activity levels (moderate to intensive exercise, Other physical activity beside exercise, Sitting time)* will be based on analysis of group mean change from baseline. Baseline group mean scores and group mean change for each secondary outcome score from baseline to all time points for the intervention and control groups and the between-group mean change at all time points will be presented as means and CI. The within and between-group change on outcomes from baseline to 24-72 hours prior to the initial physiotherapy consultation, 24 hours post initial physiotherapy consultation and three months post-baseline will be analysed according to the ITT principle using a maximum likelihood approach for mixed models adjusted for a relevant covariance structure. The models will be adjusted for baseline covariates where relevant. Baseline factors that will be analysed for potential covariate adjustment include: age, sex, educational level, employment, pain duration, number of pain sites, comorbidities, days to initial physiotherapy consultation, previous health care interventions, ÖMPSQ risk category, self-reported sick leave and analgesic medication consumption.

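### The SAP's primary model does not name the pre-consultation score (time point 2) that the protocol's model includes, which weakens its missing-at-random assumption for patients who cancel the consultation

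*SAP*

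**What the plan says.** The protocol (Analysis of primary outcomes) sets the scope of its mixed models as "Magnitude of within and between-group change on primary outcomes from baseline to 24-72 hours prior to the initial physiotherapy consultation", and then goes on to 24 hours after the consultation and three months. That is time points 2, 3 and 4.

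The SAP (Primary outcome analysis) drops the first of these: "The within and between-group change on primary outcomes from baseline to 24 hours post initial physiotherapy consultation and three months post-baseline will be analysed". Its outcome definition for each primary measure matches: "Time Frame: collected at baseline, 24 hours post initial physiotherapy consultation and at three months post-baseline". For average pain, the contrast at time point 2 is listed among the secondary outcomes: "Between group mean change in average pain intensity over time from baseline to 24 -72 hours prior to the initial physiotherapy consultation". The SAP's secondary analysis of continuous outcomes fits a maximum likelihood mixed model to the same two measures over time points 2, 3 and 4.

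On the contrasts, the documents agree. The protocol (Primary outcome measures) states: "Primary outcome analysis time points are 1) Baseline to 24 hours post initial physiotherapy consultation and 2) Baseline to three months". It adds that the two measures "will be additionally analysed as secondary outcomes for within group and between group differences for data collected at non-primary outcome time points".

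On patients who do not attend, the protocol (Missing data) states: "Patients who cancel their initial physiotherapy consultation will be excluded from the PREM analysis but will remain in the study for PROM" and register analyses. The SAP (Missing data) assumes missingness at random given the variables in the model. It allows multiple imputation or restricted maximum likelihood and lists no imputation variables.

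**The concern.** Time point 3 is timed from the consultation. A patient who cancels therefore has, by inference, no score at primary time point one. Neither document says how that value is defined or handled, yet the patient is kept in the analysis of patient-reported outcomes.

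For such a patient, the time point 2 score is the measurement closest to the missing one. It is also the one most likely to reflect why the visit was cancelled. If the primary model holds only baseline, time point 3 and month 3, its missing-at-random assumption does not condition on that score.

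At stake is the between-arm contrast at primary time point one, for both primary outcomes. There is also an avoidable ambiguity: two mixed models of the same measures, one with and one without time point 2, can each yield a time point 3 contrast, and the documents point to different ones as primary.

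**Working it through.** **1. Passages side by side.**

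| Place | Times named for the two measures |
|---|---|
| Protocol, Analysis of primary outcomes | baseline, 2, 3, 4 |
| SAP, Primary outcomes (definition) | baseline, 3, 4 |
| SAP, Primary outcome analysis | baseline, 3, 4 |
| SAP, Secondary outcome analysis (continuous) | baseline, 2, 3, 4 |

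The plan states no figure for this point, so there is none to reproduce.

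**2. When bias arises.** In each arm, with cancelled fraction p:

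arm bias = p × (mean time point 3 score predicted for cancellers − their true mean)

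contrast bias = film-arm bias − control-arm bias

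If cancelling depends on time point 2 and that score is not in the model, the bracket is not zero. If p and the bracket are the same in both arms, the contrast bias is zero.

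**3. Size for pain intensity.** The following are assumptions, not taken from the documents:
- SD 2.5 and no true effect.
- Correlations: baseline with time point 2, 0.6; time points 2 and 3, 0.8; baseline with time point 3, 0.5; month 3 with baseline 0.4, with time point 2 0.5-0.55, with time point 3 0.55-0.7.
- Logistic cancellation, more likely at lower time point 2 pain, slope 1 to 2.5 per SD.
- Month 3 answered and in the model.

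| Cancellation, control v film | Dependence on time point 2 | Bias without time point 2 (NRS points) |
|---|---|---|
| 10% v 10% | same in both arms | about 0 |
| 8% v 12% | same slope | 0.03-0.07 |
| 9% v 14% | same slope | 0.04-0.07 |
| 9% v 19% | same slope | 0.08-0.14 |
| 9% v 14% | film arm only, slope 1 | about 0.13 |
| 10% v 10% | film arm only | up to about 0.17 |

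The sign is positive, meaning too high a film-arm mean, so the bias goes against the film. With time point 2 in the model, the bias is below 0.01 throughout. Month 3 removes about a fifth of the bias: in the fifth row it is 0.161 without month 3 and 0.128 with it.

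**4. Second calculation.** Maximum likelihood on 200,000 patients per arm used the protocol's SD of 4, other assumed correlations, a true difference of about −1.0, and half or all of those missing time point 3 also missing month 3. It gave 0.07 to 0.26 points toward no effect when cancelling differed by arm. Scaled to SD 2.5: 0.07 × 2.5/4 = 0.04 and 0.26 × 2.5/4 = 0.16, in line with step 3.

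**5. Yardsticks.** With 225 per arm and SD 2.5, the baseline-adjusted standard error before losses is 2.5 × √(2/225) × √(1 − 0.5²) = 0.204. So 0.03/0.204 = 0.15 and 0.17/0.204 = 0.83 standard errors. Against the protocol's planning difference of 2 points, the range is 0.03/2 = 1.5% to 0.17/2 = 8.5%.

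**6. Precision.** With SD 4, 225 per arm and 10% missing at time point 3, adding time point 2 lowers the standard error by 0.3% to 1.7%. One case goes from 0.3428 to 0.3380. The ratio is 1.0142, and squared it is 1.029, worth 2.9% more patients.

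**The case against.** A reader might infer that the SAP changed the primary endpoints. It did not: both documents name time points 3 and 4 and make time point 2 secondary.

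A reader might also infer that the SAP excludes time point 2 data. It nowhere says so. The primary paragraph may list only the contrasts to be reported, and one model could serve the primary and secondary sections. Multiple imputation, if used, could draw on time point 2. This stands as a possible reading, but the SAP does not state it. The secondary section repeats the primary wording almost exactly and adds time point 2, so an analyst following the text would leave it out of the primary fit.

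A third tempting reading is that the result at primary time point one will be biased in the film's favour. The documents do not support this. Bias needs cancellation, or its dependence on time point 2 scores, to differ by arm, and no document shows that. The film's message that many pain problems resolve by themselves makes a difference plausible, no more. If film patients who feel better cancel more, the bias runs against the film.

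Other limits also stand:
- Maximum likelihood does not fill in values.
- For anyone who answers at three months, that score is the latest one and is in the model.
- Patients who cancel before time point 2 is sent have no such score to use.
- The protocol reports about 90% response at time points 2 and 3, so about 10% missing from all causes. The 9% v 14% and 9% v 19% cases average 11.5% and 14% from cancellation alone. The 8% v 12% case averages 10% and gives 0.03-0.07 points.
- Cancellation counts by arm are already in the SAP's CONSORT template.

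**Conclusion.** The discrepancy is real and should be resolved before the analysis. The protocol's primary model includes time point 2; the SAP's primary model and primary time frame do not name it. Read literally, the SAP sets aside a collected score for patients it keeps under intention to treat, and so rests on a weaker missing-at-random assumption than it needs.

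The consequence is conditional and modest. For pain intensity at time point 3, the bias is about 0.03-0.17 NRS points under the stated assumptions if cancellation or its dependence on time point 2 differs by arm, and about 0 if not. The upper end needs steep dependence in one arm only. Cancellation rates, correlations and the SD of 2.5 are all assumed. The size for PSEQ-10 was not calculated, though the reasoning is the same. The gain in precision is too small to be an argument by itself.

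**What to change.** In the SAP's primary outcome definitions and Primary outcome analysis, state that the maximum likelihood model for each primary outcome is fitted to baseline and time points 2, 3 and 4. This matches the protocol and the SAP's own secondary model. State that the confirmatory contrasts, and their Bonferroni adjustment, stay at time points 3 and 4 only. In Missing data, state that any multiple imputation of a primary outcome includes its time point 2 score as an imputation variable.

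The cost is a change of wording. The data are already collected and the model is already specified for the secondary analysis. The only statistical price is a slightly larger covariance matrix to estimate.
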